3.1 Subject Disposition

A subject disposition table will be presented that displays the number of subjects enrolled in addition to the number of screen failures, as well as the number subjects treated, completed, and discontinued. This table will also contain counts for each reason for premature study discontinuation. A corresponding listing of reasons for early study discontinuation will also be provided.

3.2 Demographic and Baseline Characteristics

Demographic and baseline characteristics will be summarized by the number and percentage of subjects/eyes for the categorical variables and descriptive statistics for the continuous variables.

4 Efficacy Analysis Strategy

A success on the primary effectiveness endpoint would be indicated by successful outcome on at least one of the two independent hypothesis tests (VIVITY vs. SYMFONY and/or

VIVITY vs. AT LARA). There are two independent hypotheses for each effectiveness endpoint for comparisons between 1) VIVITY vs. SYMFONY, and 2) VIVITY vs. AT LARA. There will be no comparison between the two non-Alcon comparators. The family-wise alpha of 0.05, two-sided, will be expensed equally between the two hypothesis tests, 0.025, two-sided, for each comparator.

For each VIVITY comparison between the two non-Alcon IOLs, hypothesis tests to evaluate statistical significance of the secondary effectiveness endpoints will be conducted only after a successful outcome on the primary endpoint for that IOL comparison is demonstrated. The Type I error for comparison against each comparator lens will be maintained at the 0.025, two-sided, level using a step down approach described in Section 4.4.

4.1 Efficacy Endpoints

Primary Endpoint:

- Percentage of subjects not bothered at all by halos (on the QUVID questionnaire Q2.3) at 3 months post-implantation.

[figure not shown]
Secondary Endpoints:

- Percentage of subjects not bothered at all by glare (on the QUVID questionnaire Q3.3) at 3 months post-implantation.
- Percentage of subjects not bothered at all by starbursts (on the QUVID questionnaire Q1.3) at 3 months post-implantation.

[REDACTED]

[REDACTED]

- [REDACTED]
- [REDACTED]
- [REDACTED]
- [REDACTED]
- [REDACTED]
- [REDACTED]
- [REDACTED]
- [REDACTED]
- [REDACTED]
- [REDACTED]
- [REDACTED]
- [REDACTED]

4.2 Efficacy Hypotheses

4.2.1 Primary Effectiveness Hypotheses

The primary effectiveness objective is to demonstrate the superiority of VIVITY to SYMFONY or AT LARA in % of subjects not bothered at all by halos at 3 months post bilateral implantation.

The null and alternative hypotheses in support of the primary effectiveness objective are:

$$H_0: p_{\text{Vivity}} \leq p_{\text{Comparator}}$$

$$H_A: p_{\text{Vivity}} > p_{\text{Comparator}}$$

Where p_{Vivity} and $p_{\text{Comparator}}$ refer to the percent of subjects not bothered at all by halos in the VIVITY group and the comparator groups respectively. The two comparator groups are SYMFONY and AT LARA.

4.2.2 Secondary Effectiveness Hypotheses

The secondary effectiveness objectives are to demonstrate the superiority of VIVITY to SYMFONY or AT LARA in:

- 1) % of subjects not bothered at all by glare at 3 months post bilateral implantation
- 2) % of subjects not bothered at all by starbursts at 3 months post bilateral implantation

If the primary null hypothesis is rejected for either or both comparisons to VIVITY, the following null and alternative hypotheses in support of the secondary effectiveness objectives will be tested independently for each comparator (if applicable) in the order of glare, then starburst, if glare is successful:

$$H_0: p_{\text{Vivity}} \leq p_{\text{Comparator}}$$

$$H_A: p_{\text{Vivity}} > p_{\text{Comparator}}$$

Where p_{Vivity} and $p_{\text{Comparator}}$ refer to the percent of subjects not bothered at all by glare (then starbursts in a step down manner) in the VIVITY group and the comparator groups respectively. The two comparator groups are SYMFONY and AT LARA.

[REDACTED]

[REDACTED]

[REDACTED]

4.3 Statistical Methods for Efficacy Analyses

To account for multiplicity, two sets of three hypotheses will be tested independently (eg, VIVITY vs. SYMFONY; and VIVITY vs. AT LARA) in sequence: primary hypothesis, followed by the first secondary hypothesis, followed by the second secondary hypothesis. The primary effectiveness objective is considered met if at least one pairwise comparison of the primary hypothesis is met. The type I error for each superiority test is 2.5% (2-sided). Each of the secondary hypotheses will be tested at 2.5% (2-sided).

4.3.1 Primary Effectiveness Analyses

The superiority hypothesis for each comparator will be evaluated using the Miettinen-Nurminen method (1985). The superiority hypothesis will be deemed supported if the lower limit of the two-sided 97.5% confidence interval exceeds zero. Primary analysis will be based on AAS. [REDACTED]

Success on the primary effectiveness hypothesis test will be concluded independently between VIVITY and SYMFONY, and between VIVITY and AT LARA.

[REDACTED]

[REDACTED]

[REDACTED]

[REDACTED]

[REDACTED]

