Key words	
• Cataracts• Intraocular lens• IOL• Extended depth of focus• Presbyopia• Australia• New Zealand• Visual disturbances
 	 

Table 3-1 Schedule of Study Procedures and Assessments

Visit	Visit 0	Visit 00	Visit 1	Visit 2	Visit 00A	Visit 1A	Visit 2A	Visit 3A	Visit 4A ¹	Visit 5A	Unscheduled visit
Eye	Both Eyes	1 st Eye	1 st Eye	1 st Eye	2 nd Eye	2 nd Eye	2 nd Eye	Both Eyes	Both Eyes	Both Eyes	N/A
Day Number	Day -28 to 0	Day 0	Day 1-2 Post Visit 00	Day 7-14 Post Visit 00	Day 7-21 Post Visit 00	Day 1-2 Post Visit 00A	Day 7-14 Post Visit 00A	Day 30-60 Post Visit 00A	Day 70-100 Post Visit 00A	Day 120-180 Post Visit 00A	N/A
General Assessments and Procedures											
Informed Consent	X										
Demographics	X										
Medical History	X										
Concomitant Medications	X	X	X	X	X	X	X	X	X	X	X
Inclusion/Exclusion	X										
Urine Pregnancy Test ²	X										
Ophthalmic Assessments											
Questionnaires											
• QUID (for visual disturbance)	X							X	X	X	
• [REDACTED]											
• [REDACTED]											

Printed By:

Print Date:

Visit	Visit 0	Visit 00	Visit 1	Visit 2	Visit 00A	Visit 1A	Visit 2A	Visit 3A	Visit 4A ¹	Visit 5A	Unscheduled visit
Eye	Both Eyes	1 st Eye	1 st Eye	1 st Eye	2 nd Eye	2 nd Eye	2 nd Eye	Both Eyes	Both Eyes	Both Eyes	N/A
Day Number	Day -28 to 0	Day 0	Day 1-2 Post Visit 00	Day 7-14 Post Visit 00	Day 7-21 Post Visit 00	Day 1-2 Post Visit 00A	Day 7-14 Post Visit 00A	Day 30-60 Post Visit 00A	Day 70-100 Post Visit 00A	Day 120-180 Post Visit 00A	N/A
[REDACTED]	■							■	■		
Biometry (collect all available measurements including ACD, AL, keratometry, corneal thickness, crystalline lens thickness, white-to-white)	X ³								X		
Manifest Refraction	X			X			X	X	X	X	(✓)
[REDACTED]											
[REDACTED]									■		
[REDACTED]	■			■			■	■	■	■	■
[REDACTED]									■		
[REDACTED]									■		
[REDACTED]									■		
[REDACTED]									■		

Printed By:

Print Date:

Visit	Visit 0	Visit 00	Visit 1	Visit 2	Visit 00A	Visit 1A	Visit 2A	Visit 3A	Visit 4A ¹	Visit 5A	Unscheduled visit
Eye	Both Eyes	1 st Eye	1 st Eye	1 st Eye	2 nd Eye	2 nd Eye	2 nd Eye	Both Eyes	Both Eyes	Both Eyes	N/A
Day Number	Day -28 to 0	Day 0	Day 1-2 Post Visit 00	Day 7-14 Post Visit 00	Day 7-21 Post Visit 00	Day 1-2 Post Visit 00A	Day 7-14 Post Visit 00A	Day 30-60 Post Visit 00A	Day 70-100 Post Visit 00A	Day 120-180 Post Visit 00A	N/A
[REDACTED]											
[REDACTED]									■		
[REDACTED]									■		
[REDACTED]									■		

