12.4.1.2 Analysis Methods

The superiority hypothesis for each comparator will be evaluated using a two-sample test of proportions. The null hypothesis is rejected if the 1-sided p-value is less than 0.0125. Primary analysis will be based on AAS. [REDACTED]

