4.3.2 Secondary Effectiveness Analyses

For each comparator, if the primary effectiveness hypothesis is not successful, no hypothesis test for secondary effectiveness endpoints will be further conducted for that comparator. If the primary effectiveness hypothesis is successful, hypotheses for glare will first be tested. If the hypothesis for glare is successful, the hypothesis for starbursts will be tested.

The superiority hypothesis for each comparator will be evaluated using the Miettinen-Nurminen method (1985). The superiority hypothesis will be deemed supported if the lower limit of the two-sided 97.5% confidence interval exceeds zero. Main analysis will be based on AAS. [REDACTED]

Success on the secondary hypothesis tests, sequentially for glare then starbursts, will be concluded independently for between VIVITY and SYMFONY, and between VIVITY and AT LARA.

[REDACTED]

[REDACTED]

[REDACTED]

[REDACTED]

[REDACTED]

[REDACTED]

- [REDACTED]
- [REDACTED]
- [REDACTED]
- [REDACTED]

[REDACTED]

[Redacted text block]

[Redacted text block]

[Redacted text block]

[Redacted text block]

[Redacted text block]

[Redacted text block]

[Redacted text block]

4.3.3.6 % of Subjects Responding by Category to QUID Questionnaire Items (3 and 6 months)

For AAS, the number and percentages of subjects in each category of responses to each question on the QUID questionnaire will be reported by treatment group at each visit this questionnaire is administered.

[Redacted]

[Redacted]

[Redacted]

[Redacted]

[Redacted]

[Redacted]

[REDACTED]

[REDACTED]

[REDACTED]

[REDACTED]

[REDACTED]

[REDACTED]

[REDACTED]

[REDACTED]

[REDACTED]

[REDACTED]

- | [REDACTED]
- | [REDACTED]
- | [REDACTED]

[REDACTED]

[REDACTED]

[REDACTED]

[REDACTED]

[REDACTED]

[figure not shown]
[REDACTED]

[figure not shown]
[REDACTED]

Table 4-1 summarizes the key effectiveness analyses.

Table 4–1 Summary of Analysis Strategy for Key Effectiveness Endpoints

Endpoint	Main vs. Sensitivity Approach ^a	Statistical Method ^b	Analysis Set	Missing Data Approach
Primary				
Percentage of subjects not bothered at all by halo (on the QUID questionnaire Q2.3) at 3 months	M	Miettinen-Nurminen method	AAS	Observed data only
[REDACTED]	[REDACTED]	[REDACTED]	[REDACTED]	[REDACTED]
Secondary				
Percentage of subjects not bothered at all by glare (on the QUID questionnaire Q3.3) at 3 months	M	Miettinen-Nurminen method	AAS	Observed data only
[REDACTED]	[REDACTED]	[REDACTED]	[REDACTED]	[REDACTED]

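### The main QUVID analyses leave out the preoperative answer to the same item; stratifying by it would add precision only as far as it predicts the 3-month answer

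*SAP*

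**What the plan says.** The schedule (protocol Table 3-1, repeated in SAP Table 10-1) has a row "QUID (for visual disturbance") marked at Visit 0 and again at Visits 3A, 4A and 5A. Protocol 10.2.1 also lists the questionnaire among the screening steps.

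The tested endpoints use one postoperative time point. SAP 4.1 defines the primary endpoint as "Percentage of subjects not bothered at all by halos (on the QUVID questionnaire Q2.3) at 3 months post-implantation"; glare (Q3.3) and starbursts (Q1.3) have the same form.

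Protocol 12.4.1.2 gives the method as "The superiority hypothesis for each comparator will be evaluated using a two-sample test of proportions", and 12.4.2.2 uses the same method for the secondary endpoints. SAP 4.3.1 says "The superiority hypothesis for each comparator will be evaluated using the Miettinen-Nurminen method (1985"), and 4.3.2 names the same method, both with the rule "The superiority hypothesis will be deemed supported if the lower limit of the two-sided 97.5% confidence interval exceeds zero". The main-analysis rows of SAP Table 4-1 list that method, the AAS and observed data only, for all three endpoints. No visible sentence names a covariate or stratum.

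SAP 1.3 stratifies randomization by site alone. SAP 4.3.3.6 tabulates QUVID response categories descriptively by group.

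**The concern.** How bothered a person says they are depends on the person as well as the lens. If some subjects tend to report no bother both before and after surgery, the Visit 0 answer carries information about the 3-month answer. An analysis that ignores it leaves that between-subject variation in the standard error, and leaves any chance difference between arms in the estimate.

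The stake is a single confidence limit per comparator, with about 60 completers per lens. The effect carries down the sequence, because SAP 4.3.2 says "If the primary effectiveness hypothesis is successful, hypotheses for glare will first be tested", and starbursts follow only if glare succeeds. A weaker halo test therefore also reduces the chance of reaching the secondary claims.

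**Working it through.** **Inputs from the documents.** 60 completers per arm (protocol section 8). SAP section 4: "The family-wise alpha of 0.05, two-sided, will be expensed equally between the two hypothesis tests, 0.025, two-sided, for each comparator". Protocol 12.4.1.2: "The null hypothesis is rejected if the 1-sided p-value is less than 0.0125".

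**The plan's own figures.** These reproduce. Alpha: 0.025 + 0.025 = 0.05, and 0.025 / 2 = 0.0125 one-sided, which matches the 97.5% interval. Sample size: 180 × 1.10 = 198, and 198 × 1.10 = 217.8, rounded to 218.

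**Assumptions.** The planning response rates and power are redacted, and the documents give no link between baseline and 3-month answers. I call that link the association: the within-arm difference in 3-month response between subjects unbothered and bothered at Visit 0. It is varied from 0 to 40 or 50 points.

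**Step 1: chance imbalance at baseline.** SD of the between-arm difference = √(2p(1−p)/60).
- Baseline rate 50%: √(2 × 0.5 × 0.5 / 60) = 0.091; 95% range ±1.96 × 0.091 = ±17.9 points.
- Baseline rate 20%: SD 0.073; 95% range ±14.3 points.

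**Step 2: effect on the 3-month difference.** Shift = imbalance × association.
- At the 95% limit with a 50% baseline rate: 0.179 × 0.10 = 1.8 points, 0.179 × 0.20 = 3.6, 0.179 × 0.40 = 7.2.
- At the median absolute imbalance, 0.674 × 0.091 = 6.1 points: 1.2 points (association 20) to 2.5 points (association 40).

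**Step 3: precision.** Adjusting for a covariate with within-arm correlation ρ multiplies the variance by 1 − ρ², equivalent to 60 / (1 − ρ²) subjects per arm: 60.6 at ρ = 0.1, 62.5 at 0.2, 65.9 at 0.3, 71.4 at 0.4, 80.0 at 0.5.

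**Step 4: power by simulation.** Score test at zero difference, one-sided 0.0125, 60 per arm, 45% against 70%, baseline rate 50%. Stratum weights are n₁n₂/(n₁+n₂).

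| Association (points) | Unstratified | Stratified |
|---|---|---|
| 0 | 0.70 | 0.70 |
| 10 | 0.70 | 0.71 |
| 20 | 0.70 | 0.73 |
| 30 | 0.70 | 0.75–0.76 |
| 40 | 0.70 | 0.80 |

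With 40% against 65% and a 40% baseline rate, 0.685 becomes 0.690, 0.697, 0.714 and 0.741 at associations of 0, 10, 20 and 30. With 50% against 75% and a 40% baseline rate there is a small loss at weak association: 0.734 to 0.727 at 0, and 0.734 to 0.732 at 10. It becomes a gain at 20 (0.734 to 0.748).

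**Step 5: type I error.** With both arms at 45%, the unstratified test gives about 0.011 and the stratified test 0.012 to 0.013, at every association. With both arms at 40% and a 40% baseline rate, the unstratified test gives 0.012 overall. Among trials with a baseline imbalance of at least 1 SD favouring VIVITY (about one in six), it gives 0.017, 0.031 and 0.048 at associations of 10, 30 and 50. With the opposite imbalance it gives 0.008, 0.002 and 0.0002, so the errors average out. The stratified test stays at 0.011 to 0.012 in either case.

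**The case against.** A reader might infer that the unadjusted test is biased or that its error rate is inflated. The documents do not support that. Randomization makes the raw difference unbiased, the 97.5% interval already allows for chance imbalance, and step 5 shows the overall error is held. The higher conditional rates describe trials selected for an imbalance in one direction. Imbalance and lost precision are also largely one issue seen from two sides, not two separate faults.

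The association may be weak. The Visit 0 answer describes eyes with cataract, which surgery removes, and the protocol (5.1) links visual disturbances to diffractive structures in the lens. Nothing in the documents shows that bother carries over. At 10 points the gain is about one power point. This stands, and it is why the point is conditional.

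A reader might also infer that the baseline answer is wholly unused. That goes too far. Text after the primary method in SAP 4.3.1 is redacted, as are the other rows and the footnotes of Table 4-1. The table cell does not say whether the Miettinen-Nurminen analysis is stratified, so a stratified or adjusted analysis cannot be excluded, though the protocol's two-sample test points to an unadjusted one. SAP 4.3.3.6 tabulates the questionnaire at every visit where it is given, which read literally includes Visit 0, although its heading names only 3 and 6 months. Such a table would show an imbalance but not correct for it.

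Sparse strata and cost are weaker objections. At 45% against 70%, stratifying cost no power even with a 15% baseline rate. The proposal does not address site, the randomization stratum; that is a separate question.

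**Conclusion.** The point holds as a conditional improvement, not as an error. On the visible text, the main analyses of all three tested endpoints omit a preoperative answer to the same item that the trial already collects. The gain over a starting power of about 0.70 is nil with no association, about 1 point at 10, 3 at 20, 5 to 6 at 30 and 10 at 40. It also steadies the error rate when the arms happen to differ at baseline. The downside found was at most about 0.7 of a power point, at 50% against 75% with no association.

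These sizes rest on assumed response and baseline rates and on an association the documents do not state. They do not show that the trial is underpowered, nor that an imbalance will occur.

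**What to change.** Before unmasking, amend SAP 4.3.1, 4.3.2 and Table 4-1 so that the main analysis is the stratified Miettinen-Nurminen risk difference, with stated stratum weights. Stratify by the Visit 0 answer to the same item: unbothered against any degree of bother. Each endpoint then has its own stratifier: Q2.3 for halos, Q3.3 for glare, Q1.3 for starbursts.

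State in advance where subjects with no Visit 0 answer go, and when a sparse stratum is collapsed. Keep the two-sided 97.5% interval, the requirement that its lower limit exceed zero, and the testing order. Report the unstratified result as supportive. Align the two-sample test wording in protocol 12.4.1.2 and 12.4.2.2 and in the protocol summary.

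If redacted text already makes a baseline-adjusted analysis the main one, the sponsor need only confirm it. If it is there only as a sensitivity analysis, the remaining decision is whether to promote it.

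The cost is wording in two documents and three stratifiers instead of none. No new data, visits or subjects are needed. Timing matters: adjustment added after an imbalance has been seen would carry little weight.

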4.3.2 Secondary Effectiveness Analyses

For each comparator, if the primary effectiveness hypothesis is not successful, no hypothesis test for secondary effectiveness endpoints will be further conducted for that comparator. If the primary effectiveness hypothesis is successful, hypotheses for glare will first be tested. If the hypothesis for glare is successful, the hypothesis for starbursts will be tested.

The superiority hypothesis for each comparator will be evaluated using the Miettinen-Nurminen method (1985). The superiority hypothesis will be deemed supported if the lower limit of the two-sided 97.5% confidence interval exceeds zero. Main analysis will be based on AAS. [REDACTED]

Success on the secondary hypothesis tests, sequentially for glare then starbursts, will be concluded independently for between VIVITY and SYMFONY, and between VIVITY and AT LARA.

[REDACTED]

[REDACTED]

[REDACTED]

[REDACTED]

[REDACTED]

[REDACTED]

- [REDACTED]
- [REDACTED]
- [REDACTED]
- [REDACTED]

[REDACTED]

[Redacted text block]

[Redacted text block]

[Redacted text block]

[Redacted text block]

[Redacted text block]

[Redacted text block]

[Redacted text block]

4.3.3.6 % of Subjects Responding by Category to QUID Questionnaire Items (3 and 6 months)

For AAS, the number and percentages of subjects in each category of responses to each question on the QUID questionnaire will be reported by treatment group at each visit this questionnaire is administered.

[Redacted]

[Redacted]

[Redacted]

[Redacted]

[Redacted]

[Redacted]

[REDACTED]

[REDACTED]

[REDACTED]

[REDACTED]

[REDACTED]

[REDACTED]

[REDACTED]

[REDACTED]

[REDACTED]

[REDACTED]

- | [REDACTED]
- | [REDACTED]
- | [REDACTED]

[REDACTED]

[REDACTED]

[REDACTED]

[REDACTED]

[REDACTED]

[figure not shown]
[REDACTED]

[figure not shown]
[REDACTED]

Table 4-1 summarizes the key effectiveness analyses.

Table 4–1 Summary of Analysis Strategy for Key Effectiveness Endpoints

Endpoint	Main vs. Sensitivity Approach ^a	Statistical Method ^b	Analysis Set	Missing Data Approach
Primary				
Percentage of subjects not bothered at all by halo (on the QUID questionnaire Q2.3) at 3 months	M	Miettinen-Nurminen method	AAS	Observed data only
[REDACTED]	[REDACTED]	[REDACTED]	[REDACTED]	[REDACTED]
Secondary				
Percentage of subjects not bothered at all by glare (on the QUID questionnaire Q3.3) at 3 months	M	Miettinen-Nurminen method	AAS	Observed data only
[REDACTED]	[REDACTED]	[REDACTED]	[REDACTED]	[REDACTED]
Percentage of subjects not bothered at all by starbursts (on the QUID questionnaire Q1.3) at 3 months	M	Miettinen-Nurminen method	AAS	Observed data only
[REDACTED]	[REDACTED]	[REDACTED]	[REDACTED]	[REDACTED]
[REDACTED]	[REDACTED]	[REDACTED]	[REDACTED]	[REDACTED]

4.6 Handling of Missing Data

There be no imputation for missing data. The influence of missing data is expected to be minimal.

5 Safety Analysis Strategy

5.1 Safety Endpoints

Safety endpoints are:

- Adverse events including SSIs
- Device deficiencies
- IOP (clinically significant change)
- Slit lamp exam findings
- Dilated fundus exam findings
- IOL observations including IOL tilt/decentration
- Subjective PCO assessment
- Posterior capsulotomy
- Intraoperative surgical problems
- Other procedures at surgery (combined and/or additional).

5.2 Safety Hypotheses

There are no formal safety hypotheses for this study.

5.3 Statistical Methods for Safety Analyses

The focus of the safety analysis will be a comprehensive descriptive assessment of safety endpoints listed in Section 5.1. Except otherwise stated, the analysis set for all safety analyses is the safety analysis set as defined in Section 2.3. Baseline will be defined as the last measurement prior to exposure to investigational product, except otherwise stated.

5.3.1 Adverse Events

The number and percentage of all ocular adverse events will be tabulated by preferred term with a breakdown by treatment, separately for first, second and all eyes. An eye with multiple ocular AEs of the same preferred term is only counted once toward the total of this preferred term.

Adverse events will be summarized in the following tables, by treatment group:

1. All Adverse Events (Serious and Non-Serious Combined)
 - a. Ocular
 - b. Nonocular

2. All Adverse Device Effects
 - a. Ocular
 - b. Nonocular

3. All Serious Adverse Events (including Serious Adverse Device Effects)
 - a. Ocular
 - b. Nonocular

3. Subject Listings
 - a. Non-serious Ocular
 - b. Non-serious Nonocular
 - c. Serious Ocular
 - b. Serious Nonocular

All ocular tables will be presented separately for first and second implanted eyes.

In addition, listings of adverse events will be provided. The listings will include the following variables: treatment, site, subject, eye, days from surgery, duration, adverse event description, causality, severity, seriousness, outcome and preferred term.

